9.2 Enrollment Duration

We expect to enroll 52 participants over 12 months.

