6.4 Statistical analysis of clinical success

It has been noted in the literature that if a tumor reoccurs in the same site, it typically does so within the first two years [4]. There is some evidence of reoccurrence as far out as 40 months but that is based on limited data and beyond 4 years there is no follow-up data [4]. For the purpose of this study, the analysis of the clinical outcome will be based on a 2-year endpoint. As with the determination of technical success,

a literature-based benchmark will be used in lieu of a concurrent control. Results in [5] suggest that the cumulative incidence of reoccurrence by 2 years is around 26.4% and by 4-years is around 37.8%. However, these results were not stratified by tumor size, which is known to be a very strong predictor of clinical success. In [4], reoccurrence rates of 14.1%, 24.5%, and 58.1% were reported for the small, medium and large tumor groups. However, these rates were evaluated over variable lengths of follow-up. The proportion of cases expected in the small, medium, and large categories are 12.9%, 41.9%, and 45.2% respectively (based on past clinical experience). The benchmark number to be used for the overall group comparison is the weighted average of these proportions with the above recurrence rates, which equals 24.1%. Because the failure rate data in [4] involve 1817 observations, we use this number as a basis for quantifying the precision in the baseline. Computing the lower end-point of a 95% confidence interval, we obtain $q_{\text{base}} = 0.2217$ as our ideal or most conservative benchmark against which to compare outcomes under PGP. This value is conservative even beyond the buffer provided by the allowance for uncertainty in its true value via the confidence interval end-point calculation as the follow-up times in [4] were shorter on average than 2-years.

For both the conservative and less conservative benchmarks, the overall assessment of the clinical success of PGP will be evaluated using the hypothesis test:

$$H_0: q_{\text{RFA}} \geq q_{\text{base}} \text{ against the alternative } H_1: q_{\text{RFA}} < q_{\text{base}}$$

where q_{RFA} is the probability of reoccurrence by 2-years of follow-up.

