Patients are enrolled in the study over a 2-year period. Therefore, if every patient was followed up for 2-years, the study would be 4-years long. We propose a statistical analysis plan which will allow estimating the clinical performance of the PGP at any point after the initial recruitment phase of 2 years – with increasing accuracy as the analysis approaches the 4-year mark, having access to 2-year follow up data for each patient who entered the study.

The analysis will be as follows: the investigators will check the status of patients every 6-months (data may be available every 3-months for some patients but to be safe we only assume 6-month interval data will be available) and essentially impute future status from patients' prior status. The imputations will be automatically performed by a Bayesian analysis, which assigns an unknown parameter to each participant's 6-monthly future status, through 2-years of follow-up.

The data for each patient is a 5-item multinomial random variable indicating whether they experienced recurrence before 6-months, between 6 and 12 months, between 12 and 18 months, between 18 and 24 months, or survived recurrence-free to 24 months and a covariate for the size of tumor. The four values of the multinomial outcome variable are (1,0,0,0,0) for recurrence before 6 months, (0,1,0,0,0) for recurrence between 6 and 12 months, (0,0,1,0,0) for recurrence between 12 and 18 months, (0,0,0,1,0) for recurrence between 18 and 24 months, and (0,0,0,0,1) for no recurrence in the 24-months follow up period.

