We refrain from using a Cox model or a parametric survival model to compare the status of the patients at two years of follow-up because reoccurrence status may only be known at 6-monthly intervals. Instead, we use a discrete-time survival model in which we model the probability of reoccurrence in each 6-month period thru 2-years of follow-up along with the event that the length of follow-up without reoccurrence exceeds 2-years. The dependent variable is a polytomous multinomial random variable because each patient's reoccurrence status (if followed up for the full 2 years) will be in exactly one of the 5 categories. The probabilities for the 5 categories sum to 1. The purpose of modeling the interim survival probabilities is that the interim probabilities allow the missing outcome status for patients not followed for two-years to be internally imputed during Bayesian model estimation. This approach allows for maximal use of the information in the data as all subjects are used in the analysis even if that haven't been followed up for two years (emulating what the Cox or other survival model does with continuous-time follow-up data). If we end up measuring reoccurrence status every three months, we will still pursue the described approach (but have 9 categories for the multinomial outcome as opposed to 5 categories) as the data will still not be close enough to continuous to support using the Cox model.

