6.4.6 Power for clinical success

In lieu of performing an exact power calculation under the Bayesian model specified above, we will perform an illustrative calculation based on Fisher's exact test. Allowing a type I error of 0.05, the test of the above one-sided hypotheses for q_{RFA} with a sample-size of 62 lesions will reject the null hypothesis with 80% power if $q_{\text{RFA}} < 0.105$. That is, the minimal detectable difference is a reduction of approximately 0.117 in the likelihood of tumor reoccurrence – which is an effect size in line with conservative hypotheses about the improvement in outcomes that the PGP might introduce.

Subgroup analyses (e.g., based on treated tumor size) will require larger effect sizes to retain the same level of power. However, the study is only intended to be powered for the primary analysis.

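### The SAP does not say which run of the recurrence analysis is confirmatory, so its 0.05 error rate is not secured for a test read before 2-year follow-up is complete

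*SAP*

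**What the plan says.** SAP section 6.2 names clinical success as one of two primary outcomes. Section 6.4 tests H0: q_RFA ≥ q_base, where q_RFA is the probability of recurrence by 2 years, and says that "the analysis of the clinical outcome will be based on a 2-year endpoint". Status is checked every 6 months. The analysis is meant to "allow estimating the clinical performance of the PGP at any point after the initial recruitment phase of 2 years", gaining accuracy up to month 48. Outcomes not yet seen are imputed inside the Bayesian model, so that "all subjects are used in the analysis even if that haven't been followed up for two years".

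Section 6.4.3 gives every model parameter a Normal(0, 10^6) prior. Section 6.4.4 evaluates the hypothesis as the posterior probability that q_RFA < q_base. It also reports the posterior mean, standard deviation and 95% interval.

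Section 6.4.6 does not work out the error rate or power of this Bayesian rule. It offers an exact-test calculation instead: at a one-sided type I error of 0.05, a test "with a sample-size of 62 lesions will reject the null hypothesis with 80% power if" q_RFA is below 0.105, so that "the minimal detectable difference is a reduction of approximately 0.117 in the likelihood of tumor reoccurrence".

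Neither document gives a follow-up trigger for the confirmatory test, a number of looks, a posterior cut-off or an adjustment for repeated looks. The SAP counts from a 2-year enrolment period, whereas Protocol section 9.2 states "We expect to enroll 52 participants over 12 months".

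**The concern.** The 2-year endpoint fixes what is measured on each patient. It does not fix when the trial's test is carried out. The posterior that supplies early estimates is also the one from which the test is read, so anyone following the plan as written may compare q_RFA with q_base at any time from the end of accrual to month 48.

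This opens two routes to a false claim of lower recurrence. A single early run rests on few lesions observed through months 18 to 24. And if the deciding run is not named in advance, it can be picked after several have been seen. The error rate and power in 6.4.6 cover neither case. At stake is the conclusion on one of the two outcomes that the SAP calls primary.

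**Working it through.** **1. The SAP's own figure.** Inputs from 6.4 and 6.4.6: n = 62, q_base = 0.2217, one-sided 0.05. For an exact one-sample binomial test:

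- P(X ≤ 8 | 0.2217) = 0.0483 and P(X ≤ 9 | 0.2217) = 0.0930, so the test rejects at 8 or fewer recurrences.
- P(X ≤ 8 | 0.105) = 0.8006, and 0.2217 − 0.105 = 0.1167.

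The stated 0.105, 80% and 0.117 are reproduced, for one test with all 62 outcomes known. On the same complete data, a near-flat posterior with cut-off 0.95 also rejects at 8 or fewer. That makes 0.95 a natural stand-in for the missing cut-off.

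**2. Why an early run behaves differently.** With equal 6-month hazards, h = 1 − (1 − 0.2217)^(1/4) = 0.0607, and the chance of being recurrence-free at 18 months is (1 − 0.0607)^3 = 0.829.

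- Month 30, 24-month uniform accrual: only lesions entered in the first 6 of 24 months have reached 24 months, so 62 × 0.25 × 0.829 ≈ 13 inform the last interval. The chance that none of them recurs there is (1 − 0.25 × 0.829 × 0.0607)^62 ≈ 0.46.
- Month 48: 62 × 0.829 ≈ 51 lesions inform it, and the chance of no event is (1 − 0.829 × 0.0607)^62 ≈ 0.04.

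With near-flat priors, an interval without events is estimated, and imputed, at almost zero risk.

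**3. Simulation under the null.** From the SAP: true rate 0.2217, 62 lesions, 24-month accrual (taken as uniform), 6-monthly status, and the continuation-ratio model that 6.4.5 holds in reserve. Assumed: independent lesions, equal hazards, Beta(0.001, 0.001) per interval hazard in place of the Normal(0, 10^6) logit priors, success if the posterior probability exceeds 0.95, and looks at months 30, 36, 42 and 48. The largest run had 10,000 trials (Monte Carlo standard error about 0.003). Ranges are over repeat runs.

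| Time of test | False success |
|---|---|
| Month 30 | 10.0–10.9% |
| Month 36 | 7.2–7.4% |
| Month 42 | 6.2–6.4% |
| Month 48 (all 2-year data) | 5.0–5.7% |
| Any of the four | 14.4–16.2% |

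**4. Sensitivity.**

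| Change | Early look | Any of four | Complete data |
|---|---|---|---|
| Cut-off 0.975 | 7.1–7.8% (month 30) | 10.0–11.0% | 3.0–3.5% |
| 12-month accrual, looks at 27, 30, 33, 36 | 11.6–12.0% (month 27) | 14.8–15.3% | 5.2–5.3% (month 36) |
| Front-loaded recurrences | 9.3% (month 30) | 13.3% | 5.4% |
| Back-loaded recurrences | 11.9% (month 30) | 17.7% | 4.9% |
| True rate 24.1% | 6.7–7.5% (month 30) | 9.2–10.3% | 2.4–2.6% |
| Kaplan-Meier test, log-log limits | 7.1% (month 30) | 11.3% | 4.9% |

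A Beta(0.5, 0.5) prior per interval, which is not the SAP's, gives about 0.4–0.5% at month 30 and 3.3–3.4% over four looks. A look at exactly month 24 gives 0, because no lesion has completed the last interval. A crude within-patient correlation for second lesions raises the rates slightly (12.5% at month 30, 7.0% at month 48).

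**The case against.** The strongest reply is that section 6.4 speaks of estimating performance, with accuracy growing towards month 48. On that reading early runs are estimates and the complete data set decides. It is a fair reading, and 6.4.4 supports it by reporting a mean, standard deviation and interval next to the posterior probability. It would therefore be wrong to infer that an early run can only be a test. But no sentence says that the month-48 run is the deciding one, and the hypothesis is read from the same posterior whenever it is computed.

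A reader might also infer that the plan doubles the false-positive rate at an early look and triples it over several. The documents do not support that as a statement about the plan. The SAP gives no cut-off and no look times, and it neither plans nor excludes repeated testing. The tripling needs a rule that allows a claim at any of four looks, which no section describes.

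Three further limits stand:

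- The early excess comes mainly from near-flat priors combined with few late observations. Imputation alone does not cause it, and a less diffuse prior removes most of it. The near-flat prior is, however, the one in 6.4.3.
- The primary generalized-logit model was not run; the figures come from the back-up model. Coding incomplete lesions as wholly missing would bring early rates near 0, but that contradicts imputing from prior status.
- The figures are for the boundary null. Section 6.4 sets 0.2217 as the lower confidence limit of a 24.1% benchmark, and that margin absorbs part of the excess. It gives no such protection for the less conservative benchmark, which 6.4 also plans to test.

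The enrolment mismatch is a separate inconsistency. It makes the start of the analysis window unclear but is not evidence about error rates.

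**Conclusion.** The point holds as a gap with consequences: the SAP permits an early or repeated test of recurrence against q_base, and its 0.05 and 80% apply only to a single test on complete 2-year outcomes. Under the step 3 assumptions, false success is about 10% at month 30, falls to about 5% at month 48, and is about 15% if any of four looks may count. The cut-off and look times are assumptions, so these figures illustrate what the text leaves open and are not the plan's error rate. The direction persists with a stricter cut-off, 12-month accrual, other hazard shapes and a Kaplan-Meier test. The size falls with a less diffuse prior or a true rate above q_base, and fades as follow-up completes.

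**What to change.** State in SAP section 6.4 that the confirmatory comparison with q_base is made once, when every analysed lesion has recurred, completed its 24-month assessment or been permanently lost to follow-up. Label all earlier runs descriptive, with no claim of success. Tie the timing to the last patient's follow-up instead of to a 2-year recruitment phase, and reconcile that phase with the 12 months in Protocol section 9.2. A single analysis on complete data brings the simulated false-success rate back to about 5% (0.0483 for the exact test).

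The cost is SAP wording only. The model and the early estimates stay, and no data collection is added, since 2-year follow-up is already planned for every participant. The downside is that no formal recurrence claim can be made before the last 24-month assessment.

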6.4.1 Notation for multinomial (discrete-valued) outcome

Let $y_{ij} = (y_{ij0}, y_{ij1}, y_{ij2}, y_{ij3})$ denote the multinomial outcome for the i th patient as assessed by the j th rater ($j = 1, 2$) and x_i denotes the tumor size for the i th of $n = 62$ lesions analyzed in the study.. The covariate x_i can be the actual size or a vector of categorical variables indicating whether the tumor is in that size category or the excluded baseline category (e.g., medium versus small, large versus small). If tumor-size is not included in the analysis, x_i is the empty set.

6.4.2 Model for multinomial outcome: generalized logistic regression

The distribution of y_i is multinomial with five categories:

$$y_i | \theta_i \sim \text{Multinomial}_5(1, \theta_i)$$

where $\theta_i = (\theta_{i0}, \theta_{i1}, \theta_{i2}, \theta_{i3}, \theta_{i4})$ is the vector of probabilities associated with the five possible outcomes for patient i . Models for multinomial outcomes are characterized by the way in which the elements of θ_i are mapped to the predictors. One commonly used specification is generalized logistic regression in which each component of θ_i is compared to all other components through a logit link function by supposing:

$$\theta_{ik} = \lambda_{ik} / (\lambda_{i0} + \lambda_{i1} + \lambda_{i2} + \lambda_{i3} + \lambda_{i4})$$

and $\log(\lambda_{ik}) = \gamma_k + \beta x_i$ for $k = 0, \dots, 4$. A key feature of this specification is that the Bayesian software package JAGS will impute any y_{ik} whose value is missing. To implement this feature any values of y_{ik} that are missing will be represented as NA in the analytic data set. We note that the above specification assumes the proportional odds assumption that the effects of all terms other than γ_k does not depend on k holds. This is an assumption whose legitimacy can be tested empirically.

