6.2 Statistical Design

A single-arm trial of the research PGP computer technology is proposed in which a comparison of outcomes is made to benchmarks based on prior studies. There are two primary outcomes, technical success and clinical success. Because the measurement process is drastically different for these outcomes, the statistical analysis also differs markedly for each outcome and so each is separately described. Results from Kim, et al. [5] provide the benchmark against which the *technical* success of PGP is assessed. Results from Mulier, et al. [4] provide the benchmark against which the *clinical* success of PGP is assessed. We will recruit patients with a tumor size $>2\text{cm}$, and we will categorize tumor size as small if $< 3\text{cm}$, medium if between 3cm and 5cm , and large if $> 5\text{cm}$. In our analyses for clinical outcomes, we will weight our sample to equate to the relative frequencies of small, medium and large tumors to ensure that the new trial data is relevant to the benchmark from the historical data [4]. In addition to performing overall analyses and statistical tests, we will also report estimates broken down by tumor size and other subgroups of interest.

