6.4.4 Evaluation of hypothesis test and other summaries of the posterior distribution

We wish to average the 2-year survival probability across the study patients, given by

$$q_{\text{RFA}} = 1 - n^{-1} \sum_{i=1}^n \theta_{i4}$$

where based on the above generalized logit model the probability of clinical success at 2-years for patient i is given by

$$\theta_{i4} = \frac{\exp(\gamma_4 + \beta x_i)}{\exp(\gamma_0 + \beta x_i) + \exp(\gamma_1 + \beta x_i) + \exp(\gamma_2 + \beta x_i) + \exp(\gamma_3 + \beta x_i) + \exp(\gamma_4 + \beta x_i)}$$

The posterior probability of clinical success, $\Pr(q_{\text{RFA}} < q_{\text{base}} | y_1, \dots, y_n, x_1, \dots, x_n)$, is then determined by evaluating q_{RFA} for a large number of draws from the posterior distribution of the model parameters and evaluating the Monte-Carlo average

$$\Pr(q_{\text{RFA}} < q_{\text{base}} | y_1, \dots, y_n, x_1, \dots, x_n) \cong n^{-1} \sum_{j=1}^{n_{\text{sim}}} I(q_{\text{RFA}}^j < q_{\text{base}})$$

where q_{RFA}^j denotes the value of q_{RFA} computed on the j th of n_{sim} draws of the model parameters from their joint posterior distribution. The mean, standard deviation, and 95% interval estimates of q_{RFA} will be similarly determined.

Because the chance of clinical success likely varies continuously with tumor size, we can substitute the mean tumor size for the benchmark population in [4] for x_i to essentially control for tumor size. Alternatively, we may substitute x_i with the corresponding small, medium, and large tumor size subgroup mean and in so-doing evaluate the posterior probability with closer control for the tumor size distribution. For the subgroup analyses that compare the performance of RFA-GP on the small, medium and large tumor

subgroups we may estimate $\Pr(q_{\text{RFA}} < q_{\text{base}} \mid \text{size} = s, y_1, \dots, y_n, x_1, \dots, x_n)$ separately for each subgroup $s \in \{\text{small, medium, large}\}$.

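### As written, tumour size cancels out of the clinical-success model, so the size substitution and full-data size-subgroup posteriors in SAP Section 6.4.4 cannot depend on size

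*SAP*

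**What the plan says.** SAP Section 6.4.2 models recurrence as a five-category multinomial: four 6-month recurrence intervals (k = 0 to 3) and no recurrence by 24 months (k = 4). The probabilities are `theta_ik = lambda_ik / (lambda_i0 + ... + lambda_i4)`, with `log(lambda_ik) = gamma_k + beta·x_i` for all five k. Beta has no category subscript. The text presents this as deliberate: "We note that the above specification assumes the proportional odds assumption that the effects of all terms other than" gamma_k are the same for every k. Section 6.4.3 gives each gamma_k and beta a Normal(0, 10^6) prior and sets no reference constraint. Section 6.4.4 writes out theta_i4 with `beta·x_i` in the numerator and in all five denominator terms.

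Size is optional in Section 6.4.1: "If tumor-size is not included in the analysis, x_i is the empty set". Section 6.4.4 nevertheless relies on it. It offers to replace `x_i` by the benchmark population's mean size, or by subgroup means, and "in so-doing evaluate the posterior probability with closer control for the tumor size distribution". It also proposes estimating the posterior probability of success "separately for each subgroup", in notation that conditions on all y_1..y_n and x_1..x_n.

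On the role of size, Section 6.4 says of one historical source that "these results were not stratified by tumor size, which is known to be a very strong predictor of clinical success". Section 6.2 says "we will weight our sample to equate to the relative frequencies of small, medium and large tumors", but no weight appears in the Section 6.4.4 formula for q_RFA.

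**The concern.** A covariate that adds the same amount to every log-weight of a multinomial logit has no effect on the probabilities. At least one category must be free of it, or have a different coefficient. The fault is the missing reference category, not the shared slope. The label of proportional odds does not describe this model: in a cumulative-logit model, a common slope would not cancel.

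This matters because the trial has one arm and a historical benchmark, so comparability by tumour size is central. If size is included as written:

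- results labelled as size-controlled would equal the uncontrolled ones;
- the full-data subgroup posteriors would be the same for all size groups at a given q_base;
- imputed future status for patients still in follow-up would ignore size.

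The pooled estimate would look normal and would not reveal the error.

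**Working it through.** **The plan's own power figure.** With 62 lesions, q_base = 0.2217 and one-sided alpha 0.05, an exact one-sample binomial test rejects at 8 or fewer recurrences (exact alpha 0.0483). Power at q_RFA = 0.105 is 0.8006, which matches Section 6.4.6. Size does not enter this calculation, so it is unaffected.

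**Algebra.** `theta_ik = exp(gamma_k)·exp(beta·x_i) / [exp(beta·x_i)·sum_m exp(gamma_m)] = exp(gamma_k) / sum_m exp(gamma_m)`. This is free of `x_i` and beta for continuous or categorical size. The likelihood does not contain beta, so its posterior is its prior.

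**Numerical check.** Over 10,000 random (gamma, beta) draws at assumed sizes of 2.5, 4 and 6 cm, the largest difference in any theta_ik between sizes was 1.9e-15, which is rounding error. The maximised log-likelihood on expected counts for 8/26/28 small/medium/large lesions (62 × 12.9/41.9/45.2%), assuming a constant hazard, was:

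| beta | as written | with `lambda_i4 = 1` |
|---|---|---|
| -1 | -73.80 | -98.52 |
| 0 | -73.80 | -73.80 |
| 0.6 | -73.80 | -69.39 |

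**Illustration with the historical rates in Section 6.4** (14.1/24.5/58.1%). The section gives the benchmark as "the weighted average of these proportions with the above recurrence rates, which equals 24.1" per cent, but the printed size mix does not return that figure, so both orders are shown:

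- Printed: 0.129 × 14.1 + 0.419 × 24.5 + 0.452 × 58.1 = 38.3%. Every group is fitted at 38.3%, an error of +24.2, +13.8 and -19.8 points for small, medium and large.
- Small and large weights swapped: 0.452 × 14.1 + 0.419 × 24.5 + 0.129 × 58.1 = 24.1%. Every group is fitted at 24.1%, an error of +10.0, -0.4 and -34.0 points.

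**Subgroup posteriors.** The data are whole numbers near these rates. Under near-flat priors the rate is approximately Beta(R, N-R) pooled as written, and Beta(r_s, n_s - r_s) by group with the fix and categorical size. The table gives Pr(q_RFA < 0.2217 | size):

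| Recurrences, small/medium/large | as written, every group | with the fix |
|---|---|---|
| 1/8, 6/26, 16/28 (printed mix) | 0.004 | 0.83 / 0.49 / <0.001 |
| 4/28, 6/26, 5/8 (swapped mix) | 0.37 | 0.88 / 0.49 / 0.007 |

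**Imputation.** Under a constant hazard, a lesion free of recurrence at 12 months has a 7.3/13.1/35.3% chance of recurring by 24 months, by size group. The model as written gives every lesion 20.6% (printed mix) or 12.4% (swapped). If half of every group is censored at 12 months, the pooled 2-year rate is unbiased. If 25/50/75% of small/medium/large are censored, it becomes 35.0% (printed, -3.3 points) or 22.4% (swapped, -1.7). With 75/50/25% it becomes 41.0% (+2.6 before rounding) or 26.6% (+2.5).

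**The case against.** The affected analyses are optional or secondary. Size may be left out, Section 6.4.4 words its size analyses as possibilities, and the study is powered only for the primary analysis. This stands. The finding concerns analyses that include size, and the unadjusted pooled test is intact with complete follow-up or with censoring unrelated to size.

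The one firm size adjustment is the weighting in Section 6.2. If the weights enter the likelihood, they work without `x_i`. This also stands, but the SAP does not say how they enter. Applied to the average of theta_i4 they would change nothing, because all theta_i4 are equal.

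Estimating each subgroup separately could mean refitting within it, which would restore size-specific results. The notation conditions on the full data, however, and refitting would not rescue the size substitution. Size-specific benchmarks would also make the three posteriors differ, but only through the benchmark; q_RFA itself would still not vary.

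The interim-bias figures rest on assumed size-dependent censoring. The SAP attributes incomplete follow-up to staggered enrolment and states no link to size. Those figures show only what could happen.

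The continuation-ratio model in Section 6.4.5 would not cancel if size entered its logits. It is only a fallback for computing difficulty, and no size term is written there.

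**Conclusion.** The formula is wrong as written and should be corrected before analysis. The cancellation is exact and needs no assumption beyond size being included. The size substitution then has no effect, and the full-data subgroup posteriors are identical at a given q_base. On the historical rates, fitted group rates would be wrong by up to 24.2 points (printed mix) or 34.0 points (swapped).

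Those figures assume the historical rates hold under PGP, and the posteriors apply the overall benchmark 0.2217 to each size group. They show the size of the defect and do not predict trial error. The finding does not invalidate the headline pooled comparison.

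**What to change.** 1. **Section 6.4.2:** make no recurrence the reference category, with `lambda_i4 = 1` (gamma_4 = 0 and no size term) and one beta shared by the four recurrence categories.
2. **Section 6.4.4:** rewrite `theta_i4 = 1 / (1 + sum over k = 0..3 of exp(gamma_k + beta·x_i))`.
3. **Sections 6.2 and 6.4.4:** state how the size weights enter, for example `q_RFA = sum over s of w_s·(1 - theta_4(s))`, with w_s the benchmark size frequencies. The size mix in Section 6.4 must be reconciled with the 24.1% before w_s can be fixed.
4. State whether subgroup posteriors come from this fit or from refits.
5. Replace the proportional-odds label with the assumption made: size has the same log-odds effect on each recurrence interval versus no recurrence, so timing given recurrence does not depend on size. Report recurrence timing by size group. A formal test would have little power: 62 × 0.105 = 6.5 expected recurrences, 62 × 0.241 = 14.9, or 62 × 0.383 = 23.8.

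**Cost.** A few lines of SAP text and JAGS code, with no added patients or data. Five gammas become four. The common-timing assumption is only approximate: under a constant hazard 26/28/34% of small/medium/large recurrences fall in the first 6 months, while the model forces one share (29–32%). With half of each group censored at 12 months, this moves fitted group rates by at most 1.4 points and the pooled rate by 0.1.

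**Caveat.** With categorical size and the near-flat priors, a group with no recurrences has essentially unbounded log-odds. If the historical rates are scaled proportionally to an overall 0.105 (an assumption), the chance that at least one group has none is about 78% for 8/26/28 lesions and 29% for 28/26/8. Continuous size largely avoids this; otherwise name a more informative prior. Refits by subgroup carry the same risk.

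**Alternative.** Make the Section 6.4.5 continuation-ratio model primary, with an explicit common size term and corrected eta indices (its two sets of equations number the etas differently).
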